12.1 Subject Confidentiality

Each participant will be assigned a unique, numeric identifier which will be used on all collected study information. The source document in which the unique identifier is associated with personal information will be stored in a password protected computer file to which only study personnel have access. All data will be stored on the Way to Health web-based platform database. Threats to confidentiality will be minimized by careful data collection and the private and secure web-based platform. At the conclusion of the study, all identifying information will be destroyed and all data will be

archived in a password protected folder. The web application for this study will use account-based authentication and permission systems to protect confidentiality. An investigator or statistician who logs in will be able to access only de-identified data. Only research staff will be responsible for contacting participants for study related activities (responding to questions about the study) will be able to view participant names and contact information. All of these personnel will have completed research and confidentiality (CITI) training. The system will automatically generate logs of all data queries, and these will be reviewed weekly by research staff to ensure that no unauthorized persons have gained access to identifiable information. We will implement multiple, redundant protective measures to guarantee the privacy and security of the participant data. All investigators and research staff with direct access to the identifiable data will be required to undergo annual responsible conduct of research, cybersecurity, and Health Insurance Portability and Accountability Act certification in accordance with University of Pennsylvania regulations. All data for this project will be stored on the secure/firewalled servers of the PMACS Data Center, in data files that will be protected by multiple password layers. These data servers are maintained in a guarded facility behind several locked doors, with very limited physical access rights. They are also cyber-protected by extensive firewalls and multiple layers of communication encryption. Electronic access rights are carefully controlled by University of Pennsylvania system managers. We will use highly secure methods of data encryption for all transactions involving participants financial information using a level of security comparable to what is used in commercial financial transactions. We believe this multi-layer system of data security, identical to the system protecting the University of Pennsylvania Health Systems medical records, greatly minimizes the risk of loss of privacy. All study-related emails will be sent to non-work based email addresses. Research material will be obtained from participant surveys, and the wireless scales. All participants will provide informed consent for access to these materials. Research material that is obtained will be used for research purposes only. The same procedure used for the analysis of automated data sources to ensure protection of individuals' information will be used for the survey data, in that individual identifiers will be used only for linkage purposes or to contact individuals. The study identification number, and not other identifying information, will be used on all data collection and contained in these databases. All study staff will be reminded to appreciate the confidential nature of the data collected and contained in these databases. The UPenn Biomedical Informatics Consortium (BMIC) will be the hub for the hardware and database infrastructure that will support the project and where the Way to Health web portal is based. The BMIC is a joint effort of the University of Pennsylvania's Abramson Cancer Center, the Cardiovascular Institute, the Department of Pathology, and the Leonard Davis Institute.

12.2 Subject Privacy

Privacy refers to the person's desire to control access of others to themselves. Privacy concerns people, whereas confidentiality concerns data. Describe the strategies to protect privacy giving consideration to the following: The degree to which privacy can be expected in the proposed research and the safeguards that will be put into place to respect those boundaries. The methods used to identify and contact potential participants. The settings in which an individual will be interacting with an investigator. The privacy guidelines developed by relevant professions, professional associations and scholarly disciplines (e.g., psychiatry, genetic counseling, oral history, anthropology, psychology).

With assistance from IBC, SEPTA, and the City of Philadelphia, we will advertise this as a research study of different ways to help people lose and keep off weight. The initial recruitment outreach will be facilitated by IBC, SEPTA, and the City of Philadelphia, utilizing existing communication channels (as described in the recruitment section). Interested participants will be asked to go to the Way to Health (WTH) website for prescreening and eligibility ascertainment. Screening intake will be done using the WTH website supplemented by phone support as needed, with the final step being confirmation of weight by validated employee biometric assessment data (within 4 weeks), or through participants physicians (documentation provided from the patient's outreach to their physician). During the screening intake on the WTH website, we will collect subjects names, addresses, email addresses, phone numbers, height and weight, medical history, sociodemographic data, social security numbers, and employees' biometric assessment data. All of these data will be stored in an encrypted database that conforms to applicable data security standards. Access to all such data will be limited to specifically designated research staff that will be responsible for contacting participants for follow-ups and responding to questions and concerns from participants. All communications between participants and the study website will be encrypted with SSL/HTTPs technology. Social security numbers, bank account numbers and routing numbers for all persons to whom rewards are sent will be transmitted in encrypted format to Accounts Payable, who will store the data for W-9 forms. After the social security numbers are no longer needed they will be deleted from our system.

12.3 Protection of Human Participants:

Human subjects involvement and characteristics. For the proposed study, 344 subjects with a BMI of 30 to 55 kg/m² and over the age of 18 who are full-time employees of SEPTA, IBC and the City of Philadelphia will be eligible for study. Eligibility will be determined from the study inclusion/exclusion criteria (Refer to inclusion/exclusion section of the protocol application). Exclusion criteria were limited to factors that may confound results or that make participation in a weight loss program infeasible, unsafe, or require more intensive monitoring. These exclusions include unstable heart disease, uncontrolled hypertension, kidney disease, and other serious chronic illness (e.g., transplant recipient, terminal illness). Patients with diabetes mellitus on hypoglycemic medication other than metformin will be excluded because medication adjustments and monitoring that they would require is beyond the scope of this trial. Patients on diabetes or high dose diuretic medication are excluded because these medications may require adjustment during weight loss to prevent hypoglycemia and dehydration. Women who are pregnant or breastfeeding are excluded because their energy requirements are obviously different from other individuals. Substance abuse and unstable mental illness were chosen because adherence to the intervention may be disproportionately difficult in these individuals compared with other individuals. We will exclude temps or part-time employees because lost to follow-up rates over 24 months may be high. Persons with a history of bulimia nervosa-related behaviors are excluded because they may employ these behaviors to reach their weight goals. We will also exclude potential subjects who cannot or will not give consent. No subjects will be excluded on the basis of sex or race. There will be approximately equal representation of African-Americans and Caucasians and 30%-40% men based on our recruitment experience in previous weight loss clinical trials and the demographics of the employer populations.

12.4 Cost-Effectiveness Analysis.

Participants will be asked to provide informed consent when enrolled in the research project after full explanation of the research project. For the cost- effectiveness analyses, we will not be using claims data so HIPAA authorization related to access to their medical charts will not be required. We will request access to all biometric data collected as part of employer wellness programs that study participants are part of. All participants will be over the age of 18. Women and minorities will be included.

12.5 Sources of materials.

All research material obtained from study participants will be gathered prospectively and will include weight, and subjects responses to questionnaires. We will obtain biometric information through the participants employer as this information is already collected as part of the employee wellness program. In addition, research material that is obtained will be used for research purposes only.

12.6 Potential Risks Involved in the Proposed Study.

There are minimal risks associated with providing lottery-based financial incentives and making environmental manipulations to encourage initial and maintenance of weight loss. The main risk is loss of confidentiality, which will be protected as described below. There are no potential risks associated with any other measures or data to be collected. During the consent process, we will inform subjects of the risks associated with loss of confidentiality.

12.7 Risks Involved in the Cost-Effectiveness Analysis.

As stated above, the main risk is loss of confidentiality. The immediate benefits of this study for participants are minimal; however, as mentioned, so are the risks. Overall the risk to benefit ratio is highly favorable given the long term potential of this study to significantly contribute to our knowledge of financial incentive and environmental strategies to combat obesity and their impact on health and health-related behaviors.

12.8 Adequacy of Protection from Risks Recruitment and informed consent.

With assistance from IBC, SEPTA, and the City Department of Public Health we will advertise this study as a research study of different ways to help people lose and keep off weight. Potential participants will be told that some participants will also receive financial incentives, but this feature will not be advertised, lest subjects enlist primarily for that reason. Interested participants will be asked to go to the Way to Health (WTH) website or to contact study personnel by phone for prescreening and eligibility ascertainment. Intake will be done using the WTH website supplemented by phone support as needed. Enrollment will include a description of the voluntary nature of participation, the study procedures, risks and potential benefits in detail. The enrollment procedure will provide the opportunity for potential participants to ask questions and review the consent form information with family and friends prior to making a decision to participate. Participants will be told that they do not have to answer any questions if they do not wish and can drop out of the study at any time, without affecting their medical care or the

cost of their care. They will be told that they may not benefit directly from the study and that all information will be kept strictly confidential, except as required by law.

12.9 Protection against risk.

In the event of an adverse effect necessitating medical or professional intervention, referral to the study participants primary care provider or an appropriate specialist will occur. In emergency situations when a study participant contacts one of the research personnel first, the particular research staff member will either make contact with emergency personnel or advise the study participant to do so immediately and follow up with the emergency personnel to ensure communication of the study interventions and their associated risks. Participants will be queried for potentially relevant health status changes at each data collection visit throughout follow-up. Additionally, an independent DSMB will review the clinical data routinely with safety as its primary objective. No results will be reported in a personally identifiable manner.

12.10 Electronic Data Security.

The same procedure used for the analysis of automated data sources to ensure protection of patient information will be used for the survey data, in that patient identifiers will be used only for linkage purposes or to contact patients. The study identification number, and not other identifying information, will be used on all data collection instruments. All study staff will be reminded to appreciate the confidential nature of the data collected and contained in these databases. The Penn Medicine Academic Computing Services (PMACS) will be the hub for the hardware and database infrastructure that will support the project and where the Way to Health web portal is based. PMACS provides a secure computing environment for a large volume of highly sensitive data, including clinical, genetic, socioeconomic, and financial information. Among the IT projects currently managed by PMACS are: (1) the capture and organization of complex, longitudinal clinical data via web and clinical applications portals from cancer patients enrolled in clinical trials; (2) the integration of genetic array databases and clinical data obtained from patients with cardiovascular disease; (3) computational biology and cytometry database management and analyses; (4) economic and health policy research using Medicare claims from over 40 million Medicare beneficiaries. PMACS requires all users of data or applications on PMAC servers to complete a PMACS-hosted cybersecurity awareness course annually, which stresses federal data security policies under data use agreements with the university. Curriculum includes HIPAA training and covers secure data transfer, passwords, computer security habits and knowledge of what constitutes misuse or inappropriate use of the server. We will implement multiple, redundant protective measures to guarantee the privacy and security of the participant data. All investigators and research staff with direct access to the identifiable data will be required to undergo annual responsible conduct of research, cybersecurity, and Health Insurance Portability and Accountability Act certification in accordance with University of Pennsylvania regulations. All data for this project will be stored on the secure/firewalled servers of the PMACS Data Center, in data files that will be protected by multiple password layers. These data servers are maintained in a guarded facility behind several locked doors, with very limited physical access rights. They are also cyber-protected by extensive firewalls and multiple layers of communication encryption. Electronic access rights are

carefully controlled by University of Pennsylvania system managers. We will use highly secure methods of data encryption for all transactions involving participants financial information using a level of security comparable to what is used in commercial financial transactions. We believe this multi-layer system of data security, identical to the system protecting the University of Pennsylvania Health Systems medical records, greatly minimizes the risk of loss of privacy.

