8.1 Research Design and Methods

Study participants will be obese employees recruited from three employers: SEPTA, IBC, and the City of Philadelphia. We will structure the first 6 months of the study (Phase I) as a weight loss phase in which participants will be encouraged as a weight loss goal to lose 0.5 pound per week [Note: weight loss targets for sample size calculations use kg to fit in with the literature but we will use pounds for the incentive targets, as that is what Americans are most familiar with]. Phase II (months 7-18) will consist of a period of weight loss maintenance in which participants will be able to choose a weight loss goal each month of either 0 or 0.5, pounds of weight loss per week. Phase III (months 19-24) will be a period of post-intervention follow-up concluding with an in-person weigh-in at month 24.

Participants will be randomized to either a control group (information provision and the standard wellness program at each employer along with measurement of weight at 0, 6, 12, 18, and 24 months), a lottery-based financial incentive, or a series of environmental strategies and counseling regarding food intake and physical activity, or a combination of the financial incentive and environmental strategies. Participants in the incentive arm will be eligible for daily winnings based on the weights that are transmitted using wireless scales which we will provide so that they receive daily feedback on their winnings to keep weight loss goals salient. However, we will only provide the full payments based on validation of weight measurement at 6 months intervals, taking advantage of the motivating power of loss aversion by highlighting to participants that they only receive their daily winnings if they continue to

maintain weight loss (or lose further weight) (an approach we have used with great success in previous studies).

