8.4 Key Exclusion Criteria

Exclusion criteria will be limited to factors that may confound results or that make participation in a weight loss program unfeasible, unsafe, or require more intensive monitoring, as detailed in our prior work. These exclusions include: unstable heart disease, uncontrolled hypertension, kidney disease, and other serious chronic illness (e.g., transplant recipient, terminal illness); substance abuse; bulimia nervosa or related behaviors; or diabetes medication other than metformin; pregnancy or breast feeding; contraindications to counseling about diet, physical activity, or weight reduction; unstable mental illness. Participants with diabetes on medications besides metformin are excluded because these medications may require adjustment during weight loss to prevent hypoglycemia and dehydration. Individuals unable to read consent forms or fill out surveys in English will be excluded.

9. Subject Recruitment

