10.6 Design of the Incentives

The incentive programs incorporate key aspects of optimal design, including objective and reliable confirmation of behavior change at specified intervals (weight measurement), reinforcement of the target behavior (weight maintenance) with non-drug reinforcers (incentives), large payments to reinforce the target behavior, and intermittent reinforcement. All incentive participants will receive daily feedback for 18 months; they will be given an electronic scale (accurate to ± 0.2 lbs) and given a weight loss goal for the first 6 months of 0.5 lb a week. At the beginning of Phase II and each month from months 7-18 they will be asked to set a goal of either maintaining weight loss or losing further weight (e.g. choice will be either 0, 0.5 pounds per week, with a default of 0 pounds if nothing is chosen). Inviting people to set more ambitious goals than maintenance is based on evidence that people often voluntarily commit to more ambitious goals than would be economically rational and this commitment can help them achieve those goals.

Each month we will provide each study participant with a graph on the web portal that shows a line beginning at their current weight and dropping to their target weight over the remaining months of Phase I (see Figure 4 in grant proposal, which presents a sample weight loss line for a participant who begins Phase I at 250 lbs and sets a one pound per week weight loss goal over 6 months ideal weight loss trajectory and fresh start trajectory described below.). Participants will self-monitor weights daily. Each morning before eating or drinking and after urinating, participants will weigh themselves and their weights will automatically be transmitted by the Withings Scales to the Way to Health system.

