Participants will then receive automated feedback from the system (they may choose text or email) on their progress relative to their goals and their potential earnings, helping to make the payments feel immediate. They will be told that they will receive the full amount if they meet the 6 month target for their weight (the sum of the monthly weight loss goals) but half the money if they do not. Daily monitoring provides participants with a frequent reminder of their goals, chosen because people tend to adopt a narrow frame of reference to diets, rededicating themselves each day. Daily weigh-ins should reduce binge eating by making participants constantly accountable for their weight. Monthly graphical feedback provides encouragement and a symbolic reward for slow and steady progress. Participants in the lottery arm will be eligible for a daily lottery prize with an expected value of \$3.00/day if, prior to resolution of the lottery, they reported a weight at or below their goal on the ideal weight loss trajectory in Figure 4. The lottery provides both infrequent large payoffs (a 1 in 100 chance at a \$100 reward) and frequent small payoffs (a 1 in 5 chance at a \$10 reward) since subjects are motivated by both the future (fixation on large potential winnings) and the past (how often did I win?). Subjects will be assigned a 2-digit number with two distinct digits upon entry into the study, e.g. 27. A two digit random number will be generated for each day. If the last digit includes either a 2 or 7 (a 1 in 5 chance), and the subject reported a weight at or below target weight, s/he wins \$10. If the two digits are 27 (a 1 in 100 chance) the subject wins an additional \$100. When a subject reports a weight above target, we will still generate a 2-digit daily number and tell the subject if s/he would have won the lottery that day if s/he had reported a weight at or below target. We believe that a desire to avoid the regret associated with not winning combined with learning that one would have won, had one been adherent, will motivate participants to a greater degree than only on the value of the rewards. A key aspect of the weight loss trajectory is that it can be reset monthly, a critical feature in the likely event that a participant falls short of attaining a monthly weight loss goal. To avoid discouraging such subjects, who would otherwise suddenly have to lose a lot of weight to get back on track and might decide to drop out of the study, each participant will be given the opportunity for a fresh start. The overall goals set at beginning of Phase I will stay the same, but the slope of the trajectory will adjust (i.e., steepen) such that the participant need not binge diet following a month of poor weight loss performance (see Fresh start trajectory in Figure 3, for a subject who lost 1 lb. instead of 4 lbs. in first month). Keeping the overall weight loss goal constant makes the procedure fair for participants who maintain the ideal trajectory, while adjusting the slope of the weight loss line allows for recovery from slip-ups, an approach we have used to attain minimal lost to follow-up rates of less than 10% in previous weight loss studies. To give participants frequent feedback, we will pay out 50% of winnings to date at the end of each month. To minimize falsification of weights and to utilize the amplification of motivation provided by loss aversion, the other half will be held in a virtual account and paid to participants at the end of each 6-month

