13.5 Risk/Benefit Assessment

Anticipated risks of this study should be minimal and the risk/benefit ratio is extremely favorable. Participants who are obese are at greatly increased risk of many medical problems including diabetes, hypertension, cardiovascular disease, musculoskeletal disorders, and certain cancers. Losing weight would significantly lower these risks. To minimize the chance for serious and unexpected adverse

events, study participants will be screened through exclusion criteria for any health conditions that may be exacerbated by participating in a weight loss study. Our incentives try to motivate a gradual rate of weight loss that should pose little health risk in participants with BMIs of at least 30 on enrollment. Weight loss will be monitored electronically and participants who are losing more than 5 pounds in a week, 8 pounds in two weeks or 12 pounds in four consecutive weeks will be asked to slow down the pace of their weight loss, and will be reminded that they do not receive any additional incentive for losing more than an average expected pounds per month.

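### Pregnancy is an entry exclusion, but no visible rule suspends the weight-contingent incentives if a pregnancy begins during the 18-month intervention

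*Combined protocol and SAP*

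**What the plan says.** **Entry.** Section 8.4 lists pregnancy and breastfeeding among the exclusions, which it limits to "factors that may confound results or that make participation in a weight loss program unfeasible, unsafe, or require more intensive monitoring". Section 12.3 gives the specific reason: "Women who are pregnant or breastfeeding are excluded because their energy requirements are obviously different from other individuals". Section 13.5 relies on entry screening to limit adverse events: "study participants will be screened through exclusion criteria for any health conditions that may be exacerbated by participating in a weight loss study".

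**Goals.** In Phase I the goal is a loss of 0.5 lb per week for six months. In Phase II, under section 8.1, "participants will be able to choose a weight loss goal each month of either 0 or 0.5, pounds of weight loss per week"; section 10.6 adds "with a default of 0 pounds if nothing is chosen".

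**Payments and messages (10.6).** The daily lottery pays only on days when the transmitted weight is at or below goal. On other days the system will still draw a number and "tell the subject if s/he would have won the lottery that day if s/he had reported a weight at or below target". Half of the winnings is paid monthly. The other half is held and released at the end of each six-month period only if the goal is met, with a two-pound allowance for clothing.

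**Safeguards.** Section 12.9 provides a general query about health changes at each data collection visit, and referral when an adverse effect needs care. Section 13.1 requires the investigators to report serious and unanticipated events promptly, and all adverse events to the DSMB at least twice a year. Section 13.2 has the DSMB meet every six months. Section 10.1 lets a participant contact the team or withdraw at any time. Section 13.5 asks for slower loss from "participants who are losing more than 5 pounds in a week, 8 pounds in two weeks or 12 pounds in four consecutive weeks" and says that losing faster than expected earns nothing extra.

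**The concern.** The reason given for the exclusion does not stop at randomization: energy requirements differ just as much in a pregnancy that begins in month 4. Yet the payment rules depend only on weight against goal, and the lowest goal on offer is no change. Followed to the letter, they would pay a participant whom the protocol would not have enrolled in that state for losing or not gaining weight, and would withhold winnings if she gains. The would-have-won message and the held balance are meant to work through regret and loss aversion, so the pressure is deliberate. Staff who learn of a pregnancy have no visible instruction to stop it. What is at stake is participant safety and consistent handling, not the validity of the comparison.

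**Working it through.** **1. Is there a rule?** Every mention of pregnancy or breastfeeding in the available text (8.4 and 12.3) concerns eligibility. The provisions that could apply after randomization compare as follows:

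| Provision | What triggers it | Stated action on pregnancy |
|---|---|---|
| 12.9 health query | Each data collection visit | None |
| 12.9 referral | Adverse effect needing care | None; an uncomplicated pregnancy need not trigger it |
| 13.1 reporting | Adverse, serious or unanticipated events | None |
| 13.2 DSMB | Six-monthly meetings | None |
| 10.1 withdrawal | The participant's own decision | None; treatment of held winnings not stated |
| 13.5 pace check | 5 lb in 1 week, 8 lb in 2, 12 lb in 4 | None; reacts only to rapid loss |

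**2. The plan's own lottery figure.** Inputs from 10.6 are a 1-in-5 chance of 10 dollars and a 1-in-100 chance of 100 dollars.

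(1/5 × 10) + (1/100 × 100) = 2.00 + 1.00 = 3.00 dollars per on-target day, which matches the stated value.

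**3. Money tied to the weigh-in.** Half is held: 3.00 / 2 = 1.50 dollars expected per on-target day.

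- 182 on-target days (a full six-month period): 182 × 1.50 = 273 dollars. This is the ceiling on the expected value.
- 91 on-target days, then above target: 91 × 1.50 = 136.50, about 137 dollars.

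Days above target add nothing, so a participant who gains has less at risk.

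**4. How late the routine query can be.** Inputs are the visit windows in 10.5, taking six months as 26 weeks.

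- Baseline to the latest month-6 visit: 26 + 4 = 30 weeks.
- Earliest month-6 visit to latest month-12 visit, or earliest month-12 to latest month-18: 26 + 2 + 6 = 34 weeks.

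**5. Who could be affected.** The two lottery arms hold half of 344, or 172 people. Section 12.3 expects 30% to 40% men, hence 60% to 70% women: 172 × 0.60 = 103 and 172 × 0.70 = 120. These are all women in those arms at any age. The documents give no age distribution and no pregnancy rate, so the number of pregnancies cannot be calculated. In the environmental arm no lottery money is at stake.

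**The case against.** The strongest reply is that the argument rests on silence. Nothing states that incentives continue in pregnancy, and staff who were told might well stop them. The consent pages, Table 1, the wording of the visit query and a stretch of text in the last part of section 12 were not available, so an instruction could sit there. This stands, and it limits the point to the visible rules.

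The reply can add that the safety net is wider than the health query: investigators must report unanticipated events and keep risks low, and faster loss earns no extra incentive. Also true, but none of this tells anyone to suspend a goal or payment. The sums are modest too: half of the winnings is paid monthly whatever happens at the weigh-in, visit payments do not depend on weight, and the Phase II default is maintenance.

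A reader might infer more than the documents support:

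- *That the protocol judged pregnancy unsafe.* Its stated reason is energy requirements, and the general criterion in 8.4 lists confounding and feasibility as alternatives to safety.
- *That the fresh start adds pressure on a pregnant participant.* With three months of Phase I left, a participant still at baseline weight faces 13 lb (26 × 0.5) over 13 weeks, or 1.0 lb per week. That slope applies to anyone who has not lost weight. She is already 6.5 lb above the original line (13 × 0.5), so a new line from her current weight eases the immediate target.
- *That the primary result is biased or underpowered.* Analyzing the measured 18-month weight by randomized arm is a legitimate intent-to-treat choice, and with no pregnancy rate in the documents no such effect can be shown.

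**Conclusion.** The gap is real within the visible text and should be closed as a safety and completeness matter. The weight-contingent rules run for 18 months in a sample expected to be 60% to 70% women, with no stated suspension for a condition barred at entry. Up to about 273 dollars in expected held winnings per six-month period depends on a weigh-in that makes no allowance for pregnancy. The routine query may be 30 to 34 weeks after the previous visit.

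This rests on a literal reading of 10.6 and on there being no rule in the material not supplied. The number of women affected is unknown; 103 to 120 is only an upper bound for the two lottery arms. The point supports no conclusion about bias, power or the primary analysis.

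**What to change.** 1. **Section 12.9.** Name pregnancy and breastfeeding in the existing visit query, in all four arms. Ask participants to report a pregnancy between visits through the contact route already described in 10.1.
2. **Section 10.6.** On report, suspend the weight goals, the weight-contingent lottery and the would-have-won messages while she is pregnant or breastfeeding. Settle winnings already accrued without a further weigh-in condition. She stays in her randomized arm, and visits and visit payments continue.
3. **Section 11.1.** No change to the intent-to-treat analysis.

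The cost is two named items in an existing query, one reporting instruction and one suspension rule. There are two downsides. Settlement would rest on self-report, although the weigh-in condition exists partly to deter falsified weights; exposure is limited to the held winnings of the current period, about 273 dollars expected at most. Suspension also removes a chance worth up to 3 dollars a day in expectation, which may discourage reporting by a participant still on target.

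If a document not supplied already contains such a rule, a cross-reference in 10.6 and 12.9 is enough.
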